- 1.6 *Does EAA influence markers of mitochondria function vs. Placebo?*
- 1.7 *Does statin use influence cell respiration over time?*
- 1.8 *Does EAA affect primary cell derived myocyte function over time?*
- **Specific Aim #2 (Physiology): Determine if short-term prevention of atrophy, weakness, and functional mobility leads to positive changes in muscle cell structure and function, and quality of life in the long term (6 months post-TKA) vs. Placebo.**
Successful completion of Aim 2 will identify a role for EAA supplementation in clinical settings using a mechanistic approach. Our approach is based on strong preliminary clinical data from older men and women following TKA demonstrating that EAA supplementation for 1 week prior to, and for 2 week post-TKA was effective in preventing significant muscle atrophy (37). However, our preliminary data suggest that in the EAA group, atrophy at 2 weeks post-TKA was half that at 6 weeks in the operative quadriceps and hamstrings. This potential 'catch-up' muscle loss was not observed in the non-operative leg within the EAA group but was identical to the change from 2 weeks to 6 weeks in the operative leg of the Placebo group. We interpret these data to support the need to supplement for 6 weeks post-TKA in order to maximally prevent bilateral muscle atrophy.

The proposed research design will answer the following questions:

- 2.1 *Does EAA prevent short-term (7 wk post-TKA) bilateral muscle atrophy, preserve quadriceps strength, and accelerate the return of functional mobility vs. Placebo?*
- 2.2 *Are there short-term sex differences on the above outcome measures?*
- 2.3 *Will EAA increase long-term (6 mo post-TKA) quadriceps functional mobility vs. Placebo?*
- 2.4 *Does EAA improve longer-term (6 mo post-TKA) functional mobility and measures of quality of life vs. Placebo?*
- 2.5 *Are there long-term sex differences in functional mobility or measures of quality of life?*
- 2.6 *Does inhibition of angiogenic factors (IFG-1 & VEGF) inhibit a pro-angiogenic response?*
- 2.7 *Does EAA influence markers of inflammation vs. Placebo?*
- 2.8 *Does EAA influence markers of mitochondrial function vs. Placebo?*
- 2.9 *Does statin use influence cell respiration over time?*
- 2.10 *Does EAA affect primary cell derived myocyte function over time?*

Methods, Materials and Analysis

Study Design.

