**Inpatient Research Protocol & Integration w/ Standard Patient Care: Protocol while subject is inpatient (IP) on orthopedic floor (estimate 2 to 3 days as IP); Daily AM fasting blood draw by phlebotomist on POD 0 and POD 2. (leave blood on ice, research staff to pick up); Subject to don accelerometer at all times; Twice daily ingestion of supplement (subject and investigators are blinded to treatment group); Ingestion will occur 1 hour after daily physical therapy; Inpatient physical therapy to begin at 9 AM and 1 PM. Therapy per MD/PT standard Tx; Twice daily ingestion of deuterium oxide (D₂O); Daily food-log recordings (all nutrient intake) by subject. Research staff and nursing to remind subject to complete this task.

Specific Aim #2 (Physiology).

Aim #2 - Determine if short-term prevention of atrophy, weakness, and functional mobility leads to positive changes in muscle cell structure and function, and quality of life in the long term (6 months post-TKA) vs. Placebo.

Randomization Assignments.

- Aim #2, Trial #1 enrolled 19 patients before closing enrollment in June 2018. Please refer to the Event Form submitted on June 4, 2018 for additional details. Please refer to study protocol December 2017 for information on Aim #2, Trial #1 EAA proportions and protocols.
- Aim #2, Trial #2 (reflected throughout the protocol as "Aim 2") will consist of 2 groups (N=40/group through protocol completion; EAA vs. Placebo) that are identical in protocol design. Up to 160 patients will be consented to achieve 40 per group completion.

Summary of Study-Related Activities.

- Patient questionnaires before and after surgery
- Functional mobility tests before and after surgery
- Accelerometer before surgery and after surgery
- Optional muscle biopsy before and after surgery

Changes to Study-Related Activities.

Omitted Procedures or Measures for Participants Enrolled in Aim #2

- No strength & central activation testing
- No consumption of heavy water (D₂O)
- No muscle biopsies at surgery, 1 week or 2 weeks post-TKA operation
- No blood draws
- No MRIs performed
- No Three day food diary
- Removal of 6 minute walk
- Removal of study questionnaires at 2 weeks post-TKA (functional testing remains)

New or Altered Study Procedures or Measures for Participants Enrolled in Aim #2.

- New study assessment time points: 3 months & 6 months
- Optional (patient choice at enrollment) muscle biopsies at pre-op, 6 weeks & 6 months post-TKA

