- Subject demonstrates clinically relevant change in liver or renal parameters, as confirmed by a minimum of one additional repeat comprehensive metabolic panel, occurring no less than 12 and no greater than 24 hours following initial report.
- Subject demonstrates clinically relevant change in vital signs if technical failure or human error can be excluded, supported by at least two clinically relevant measures.

Criterion #4 – Cohort-level study stop.

All serious adverse events will be reported to the DSMB and IRBs within 24 hours of any member of the study team becoming aware of the adverse event.

The following will be assessed in consideration of complete trial discontinuation:

1. The types of adverse events
2. Individual-level adverse event frequency and intensity
3. Ability to effectively monitor observed adverse events in current and future patients
4. Reversibility of adverse events and possible outcomes
5. The number of subjects who experience (a) the same adverse event and (b) any adverse events
6. Medication assignment among subjects who experience (a) the same adverse event and (b) any adverse events

Stopping Rules Adapted from: Sibille M, Patat A, Caplian H & Donazzolo Y. A safety grading scale to support dose escalation and define stopping rules for healthy subjects first entry into man studies. British J Clin Pharm 2010; 70(5): 736-748.

Data Collection.

Patient data for all study-related activities will be maintained on paper source documents stored in the Slocum Foundation office at the Slocum Center for Orthopedics & Sports Medicine. Each patient will have a dedicated patient binder for tracking all study-related activities. Data will be abstracted from the paper source documents and/or electronic health records (Slocum Center and PeaceHealth) and entered onto an electronic spread sheet (e-Case Report Form, CRF). Data abstracted onto the eCRF will include a patient identifier (no names) and all data points captured during the patient's enrollment.

The following source documents will be updated and reviewed with the patient at each study time point:

- Health history, new health events (updated by study coordinators)
- Medication log (updated by study coordinators)
- Study medication log (completed by patient)
- D₂O intake log (completed by patient, Aim #1 only)

The study logs can be reviewed in Appendix 2.

Sources of Materials.

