and attrition when conducting a clinical trial. Our subjects are older adults who are undergoing a major operation. However, our preliminary studies are evidence that we are very experienced with this patient population. The average number of TKA patients who complete our studies is 3-5/mo. We are therefore very confident that we will be able to complete studies on 40 TKA patients (Aim 1) and 80 TKA patients (Aim 2); 120 over the entire 5 year study. Issues that present potentially unique problems to our longer-term study are addressed below.

Statins. A potential limitation with long-term muscle cell function of our clinical study is concurrent use of statins, which have a strong potential to compromise muscle mitochondrial function (7, 68, 109, 117). Over 50% of our TKA subjects use statins. Mitochondrial dysfunction may introduce sample bias as well as negatively impact short and longer-term function. To account for this, we propose to measure mitochondrial respiration using the Orophorus O2k respirometer, and normalize results statistically and use the non-operative leg as internal control. Thus, measuring mitochondrial respiration will allow us to determine the effects of muscle preservation and accelerated recovery of functional mobility (EAA) while accounting for statin use between groups as well as between sex and over time statistically.

Research Population & Recruitment Methods

Study populations for Aim #1 and Aim #2 are identical. In addition, the recruitment process does not differ between the short-term, biochemistry study (Aim #1) and the longer term, physiologic study (Aim #2).

Target Population.

Both aims will target older adults, ages 50 – 80 years (Aim 1) and 40 – 80 years (Aim 2) who have elected to undergo primary total knee arthroplasty performed at PeaceHealth Sacred Heart Medical Center at RiverBend or Slocum Ambulatory Surgery Center by [name], [name], [name] or [name]. Between 2005-2010, they performed a total 2,066 TKAs. Of those, 1,406 of the patients were between 50-80 years of age (68%). A total of 120 subjects will be enrolled in the two study aims.

- **Aim #1.** The biochemistry study aim will obtain complete data on **40 subjects**, randomized to either EAA supplementation or placebo, and further randomized to receive 1 week or 2 week post-surgical biopsies. Randomization is stratified by gender. Up to 70 subjects will be enrolled to account for withdrawal and attrition.

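### Statin use is to be accounted for through mitochondrial respiration, a poor proxy that is itself an EAA outcome and is missing for Aim 2 patients without biopsies; recorded baseline statin use should be the covariate

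*Combined protocol and SAP*

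**What the plan says.** The Statins paragraph of Potential Limitations gives the prevalence, "Over 50% of our TKA subjects use statins", and warns that mitochondrial dysfunction could bias the sample and impair function. Its remedy is: "we propose to measure mitochondrial respiration using the Orophorus O2k respirometer, and normalize results statistically". The non-operative leg serves as the control. It then states the purpose: "measuring mitochondrial respiration will allow us to determine the effects of muscle preservation and accelerated recovery of functional mobility (EAA) while accounting for statin use". The paragraph adds that this covers comparisons by group, by sex and over time.

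Other sections bear on this:

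- **Respiration as an outcome.** The Hypothesis section expects EAA to change respiration at 6 months. Question 2.8 asks "Does EAA influence markers of mitochondrial function vs. Placebo", and question 1.6 asks the same for Aim 1. Questions 1.7 and 2.9 ask whether statin use affects cell respiration.
- **Source of the data.** Respiration is measured only in biopsy tissue (Mitochondrial respiration, under Primary Biochemical Outcome Measures). For Aim 2 the biopsies are "Optional (patient choice at enrollment) muscle biopsies at pre-op, 6 weeks & 6 months post-TKA". The Aim 2 schedule closes them to patients enrolled within 4 weeks of surgery, and the eligibility criteria close them to patients on oral blood thinners.
- **Models.** The covariates listed under Power analyses are sex, age, body mass index, tourniquet time and macronutrient intake. Neither statin use nor respiration is among them.
- **Direct record of statins.** Coordinators keep a medication log, reviewed with the patient at each time point (Data Collection). Appendix 1 lists medication name, dose and start and stop dates for both aims as possible covariates.

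**The concern.** The nuisance factor is statin use, a patient characteristic that is already recorded. The plan handles it through a laboratory measure that statins may affect, but that EAA is also expected to affect. Adjusting a treatment comparison for a variable measured after treatment starts, and possibly changed by treatment, removes the part of the effect that passes through that variable. Functional mobility is among the primary outcomes of Aim 2, so that is where the removal would matter most.

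Coverage is the second difficulty. A statin adjustment that works through respiration cannot reach an Aim 2 patient who has no biopsy. Those patients are not a random subset: they declined, enrolled late or take blood thinners.

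**Working it through.** The plan gives no figure for this point, so the check is mainly a comparison of passages. The two calculations in steps 4 and 5 are illustrations.

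**1. What could be normalised, and by what.** The Statins paragraph does not say which results are normalised, by which variable, or at which visit. Two readings are open.

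- *Narrow:* the respiration results themselves are normalised, for example to the other leg. Functional outcomes then have no stated statin adjustment.
- *Broad:* functional results are adjusted for respiration, as the purpose sentence suggests.

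On neither reading is statin use accounted for in Aim 2 patients without a biopsy.

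**2. Is there a pre-treatment respiration value?**

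| | First biopsy | Supplement start | Pre-treatment value? |
|---|---|---|---|
| Aim 1 | in the operating room, day 0 | 1 week before surgery | no, for any patient |
| Aim 2 | at least 4 weeks before surgery | 1 week before surgery | yes, biopsied patients only |

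**3. The non-operative leg.** Statins and the supplement are both systemic. A between-leg contrast takes out what the legs share, statin and EAA effects alike, so it cannot remove one and keep the other. Timed up-and-go, stair and walking tests have no contralateral value at all.

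**4. Effect removed if post-treatment respiration is a covariate.** Let *a* be the EAA effect on respiration (SD) and *b* the slope of function on respiration (SD per SD). Then

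adjusted d = total d − a × b.

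The total d = 1.01 is the plan's average Aim 2 effect (Power calculations). The values of *a* (0 to 0.8) and *b* (0.2 to 0.6) are assumptions.

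- a = 0: 1.01 − 0 = 1.01 (nothing removed)
- a = 0.5, b = 0.4: 1.01 − 0.20 = 0.81 (20% removed)
- a = 0.8, b = 0.6: 1.01 − 0.48 = 0.53 (48% removed)

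Simulations with 400,000 subjects at a = 0.5 and b = 0.4 gave an estimated EAA effect of 1.01 unadjusted, 1.01 adjusted for statin use, 1.01 adjusted for pre-treatment respiration, 0.81 adjusted for post-treatment respiration and 0.91 adjusted for change in respiration.

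**5. Patients lost if a respiration value is required (Aim 2).** The plan states a detectable d of .79 at 40 completers per group, 85% power and two-sided α of .05. This does not reproduce: (1.960 + 1.036) × √(2/40) = 0.670, or 0.678 with the noncentral t. The stated value fits 30 per group (0.787). That mismatch is a separate matter, so the table below uses the recomputed values. The number of patients biopsied is not given; the shares are assumptions.

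| Share biopsied | n per group | Detectable d, 85% power, no covariate | Power at d = .79 | Power at d = 1.01 |
|---|---|---|---|---|
| 100% | 40 | 0.68 | 94% | 99% |
| 75% | 30 | 0.79 | 85% | 97% |
| 50% | 20 | 0.97 | 68% | 88% |
| 25% | 10 | 1.42 | 39% | 57% |

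**The case against.** The best defence is that the plan never says functional results are normalised to respiration. The same sentence also appears in the assay description, where the results most naturally mean the respiration results. Elsewhere in the protocol, cell area and respiration are expressed relative to the non-operative leg, which makes sense for a leg-specific tissue measure and not for a walking test. The listed ANCOVA covariates do not include respiration, so that model drops nobody. The Aim 2 pre-operative biopsy precedes the supplement, and adjusting for it would leave the EAA effect intact. Because EAA is randomised, omitting statin use does not bias the comparison in expectation; including it is a matter of precision. Finally, medications are already listed as possible covariates.

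All of this stands, and it rules out a stronger reading. A reader might infer that the plan will subtract part of the EAA benefit and confine Aim 2 to biopsied patients, with a heavy loss of power. The documents do not commit to such a model. Nor do they support a power figure. Removing 25% to 50% of d = .68 leaves .51 to .34 and power of 62% to 32% at 40 per group. The same shares of the plan's anticipated 1.01 leave .76 to .51 and power of 92% to 61%. These powers also ignore any gain in precision from a prognostic covariate.

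The defence does not rescue the proxy. The purpose sentence ties measured respiration to the EAA effect on mobility, and no model is given in which statin use itself appears.

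**Conclusion.** The point holds as a weakness in the chosen method. Respiration cannot account for statin use in Aim 2 patients without biopsies on any reading. In Aim 1 it has no pre-treatment value, and in both aims it is an outcome that EAA is hypothesised to change. The control leg does not solve this.

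The harm to the EAA estimate is conditional. Bias requires that post-treatment respiration be used to adjust muscle or functional outcomes, that EAA change respiration, and that this change carry through to the outcome. Loss of patients requires a model that needs a respiration value. The size of either loss cannot be computed from the documents; the ranges in the working rest on assumed associations and assumed biopsy shares. The change is worth making because a better variable is already recorded for every patient.

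**What to change.** In Data Analysis (where the covariates are listed) and in the Statins paragraph of Potential Limitations:

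- Prespecify baseline statin use (yes/no, from the medication log, before the first supplement dose) as a covariate in the functional-mobility and respiration models, for all randomised patients with the outcome.
- State that muscle and functional outcomes are not adjusted for respiration measured after supplement start.
- Keep respiration as an outcome for questions 1.6, 1.7, 2.8 and 2.9. If its role in the functional effect is of interest, label that an exploratory mediation analysis.

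The cost is a few sentences and one degree of freedom per model. No new data are needed, since medication names and dates are already collected in both aims.

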- **Aim #2.** The physiology study will obtain complete data on **80 additional subjects**, randomized to either EAA supplementation or placebo. Up to 160 subjects will be enrolled to account for withdrawal and attrition.

The target population will not include pregnant women as the study population are patients who have scheduled a total knee arthroplasty. Patients will not be scheduled for surgery if they are pregnant as per standard of care. The point in which study coordinators approach patient for recruitment, they have already been scheduled for TKA. Furthermore, women of potential childbearing age will be asked if they are or could possibly be pregnant. A hormone pregnancy test will be administered to those women who cannot verify pregnancy status prior to ingestion of amino acid supplement. Women who are surgically sterile (e.g., hysterectomy); or who are otherwise incapable of pregnancy (e.g. menopause) will not have to undergo pregnancy testing.

Inclusion & Exclusion Criteria.

Study Aim #1

Inclusion Criteria.

- Patient is 50 – 80 years old
- Patient is having a primary, unilateral TKA
- Patient has signed the current, IRB approved informed consent document

Exclusion Criteria.

- Patient has previous TKA and/or total hip arthroplasty surgery on ipsilateral lower extremity.
- Patient has previous TKA on contralateral leg
- In the judgment of the physicians the patient is not anticipated to have contralateral TKA before end of treatment is completed (6 weeks Aim #1)
- Patient has dementia or related mental issues that may potentially put the subject at risk as determined by the surgeon.
- Patient has untreated endocrine disease (hypo/hyper thyroidism, Addison's Disease or Cushing's syndrome, etc.)
- Patient has uncontrolled diabetes; defined by lab result of hemoglobin A1c level > 8.0 mg/dL at the pre-anesthesia testing visit, which must occur before the patient begins the study medication or heavy water ingestion.
- Patient has significant heart, liver, kidney or respiratory disease.
- Patient has peripheral vascular disease.
- Patient has active cancer.
- Patient has taken anabolic steroids in the prior six months.
- Patient has known current alcohol or drug abuse.
- Patient has conditions that prohibit Magnetic Resonance Imaging (MRI).
- Patient discharge status is known to be to care facility.
- Patient is on oral blood thinner such as Warfarin, Coumadin, Eliquis, etc.

Study Aim #2

Inclusion Criteria – Biopsy Participant.

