- Patient is 40 – 80 years old
- Patient is having a primary, unilateral TKA
- Patient has signed the current, IRB approved informed consent document
- Patient can schedule pre-operative biopsy at least 4 weeks prior to date of TKA

Exclusion Criteria – Biopsy Participant.

- In the judgment of the physicians the patient is not anticipated to have other lower extremity total joint arthroplasty before end of treatment is completed (6 months).
- Patient has had previous lower extremity total joint arthroplasty surgery within 6 months of starting -8 week to -1 week (+1 day) study activities.
- Patient has dementia or related mental issues that may potentially put the subject at risk as determined by the surgeon.
- Patient has untreated endocrine disease (hypo/hyper thyroidism, Addison's Disease or Cushing's syndrome, etc.)

- Patient has uncontrolled diabetes; defined by lab result of hemoglobin A1c level > 8.0 mg/dL. ~~at~~ If the patient has consented to biopsies, confirmation of the first step (below) must occur before patient can have pre-operative biopsy. Two-step verification process for this will occur; (1) patient self-report, with the addition of any available medical records Slocum Orthopedics has regarding patient diabetic status, and (2) Upon completion of standard of care pre-operative blood draw, we will confirm results of HbA1c. If the patient has not consented to have biopsies, the same verification process will occur before the patient begins taking the supplement.
- Patient has significant heart, liver, kidney or respiratory disease.
- Patient has peripheral vascular disease.
- Patient has active cancer.
- Patient has taken anabolic steroids in the prior six months.
- Patient has known current alcohol or drug abuse.
- Patient discharge status is known to be to care facility.
- Patient is on oral blood thinner such as Warfarin, Coumadin, Eliquis, etc.

Inclusion Criteria – Non-Biopsy Participant

- Patient is 40 – 80 years old
- Patient is having a primary, unilateral TKA
- Patient has signed the current, IRB approved informed consent document

Exclusion Criteria – Non-Biopsy Participant

- In the judgment of the physicians the patient is not anticipated to have other lower extremity total joint arthroplasty before end of treatment is completed (6 months).
- Patient has had previous lower extremity total joint arthroplasty surgery within 6 months of starting -8 to -1 week (+ 1 day) study activities.

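### Both Aim 2 exclusion lists contain a negated criterion on further joint replacement that, read literally, excludes patients with none anticipated and does not exclude those with one anticipated

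*Combined protocol and SAP*

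**What the plan says.** Study Aim #2 has two exclusion lists, headed "Exclusion Criteria – Biopsy Participant" and "Exclusion Criteria – Non-Biopsy Participant". The first bullet in each is identical: as the physicians judge it, "the patient is not anticipated to have other lower extremity total joint arthroplasty before end of treatment is completed". A parenthesis sets the horizon at 6 months.

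The Study Aim #1 exclusion list has a parallel bullet, narrower in scope and shorter in horizon: "the patient is not anticipated to have contralateral TKA before end of treatment is completed", with 6 weeks in the parenthesis.

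Three other statements bear on what the bullet is meant to do:

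- The inclusion lists require that "Patient is having a primary, unilateral TKA".
- The next exclusion in both Aim 2 lists is worded in the ordinary direction: "Patient has had previous lower extremity total joint arthroplasty surgery within 6 months of starting" the pre-operative study activities.
- Under Potential Limitations (Statins), the plan for mitochondrial respiration is to "use the non-operative leg as internal control". The Aim 1 outcome descriptions use the other leg in the same way for muscle cell structure and respiration.

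The Informed Consent Process section makes surgeons responsible for approving entry against the inclusion and exclusion criteria. Participant Recruitment has coordinators or physician co-investigators screen formally against them. The January 2019 amendment was submitted to divide these criteria into biopsy and non-biopsy lists, so the bullet stands in current, operative text.

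**The concern.** An exclusion criterion names a condition that makes a patient ineligible. Here the condition is the absence of an anticipated further arthroplasty, which is the state the trial appears to want. The sentence reads like an inclusion criterion placed in the wrong list.

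The bullet matters because it is the plan's only prospective safeguard against a second replacement during follow-up. The primary outcomes for Aim 2 are the functional tests and patient-reported measures, followed to 6 months. A further hip or knee replacement in that window could change timed up-and-go, stair, chair-stand and KOOS results whatever the assigned supplement. The withdrawal and stopping rules do not address a second arthroplasty, and Data Analysis does not say how measurements taken after one are handled. Appendix 1 records additional procedures and reoperation, but only as general analysis variables.

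**Working it through.** No arithmetic applies. The check is to read each occurrence under its heading and compare it with the rest of the design.

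**Step 1: the literal rule.** Exclude the patient if the bullet's statement is true.

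| Physicians' judgment | Bullet's statement | Result under this bullet |
|---|---|---|
| No further arthroplasty anticipated | True | Excluded |
| Further arthroplasty anticipated | False | Not excluded |

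The table holds for both Aim 2 lists (any other lower-limb joint replacement, 6 months) and for the Aim 1 list (contralateral TKA, 6 weeks).

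**Step 2: comparison with the rest of the design.**

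- The inclusion criterion describes a single-knee procedure. A rule admitting only patients with another replacement ahead of them does not fit it.
- The adjacent Aim 2 exclusion treats a recent replacement as a reason to keep a patient out. The Aim 1 list likewise excludes a previous contralateral TKA. It would be odd to bar a past replacement and require an upcoming one.
- The internal-control comparison needs a leg that is not operated on during the study.

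All three point against the literal rule. No other section restates the criterion in the opposite direction or corrects it.

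**Step 3: consequences under each reading.**

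- *Literal use.* Patients with no further arthroplasty anticipated are excluded. Those left eligible by this bullet carry an anticipated second operation into a 6-month follow-up. If that operation is on the contralateral leg of a participant who has biopsies, the internal-control comparison is affected as well.
- *Intended use.* Patients with no further arthroplasty anticipated are enrolled although they meet a written exclusion. The approved document and practice then disagree, and a monitor cannot confirm eligibility from the text.

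**Step 4: size.** The documents give no rate of second arthroplasty within 6 months, so the effect under literal use cannot be quantified.

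**Step 5: a related wording conflict in the same bullet.** The bullet puts the end of treatment at 6 months. The Project Summary has supplementation running through six weeks after TKA, and the Aim #2 Study Activities Timeline has follow-up running to 6 months. These passages need to be reconciled.

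**The case against.** The strongest reply is that only one reading is workable. The criterion is a physician's judgment, applied by surgeons who would understand its purpose, and the surrounding criteria make that purpose plain. The error does not touch randomization, the analysis model, alpha or power. Nothing ties the judgment to treatment arm, so no between-arm bias follows from it. Reported recruitment is also hard to square with literal use: the Aim 2 website text describes Aim 1 as completed in 2016 with 40 patients (39 under Potential Research Benefits), and Aim 2 Trial 1 enrolled 19. The wording in force at those enrolments is not visible, so this evidence is indirect.

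Most of this stands. It supports calling the bullet a drafting error, and it limits what can be claimed. It does not make the sentence usable as written: surgeons are asked to certify against the text, and the text gives the opposite of the evident intent.

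A reader might go further in three ways that the documents do not support:

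- *That the wrong patients were enrolled.* Nothing shows literal application.
- *That all 80 planned Aim 2 completers would be reportable protocol violations.* The deviation form in Appendix 2 sends a violation to the IRB and DSMB only if the event raised risk, reduced benefit, or affected rights, safety, welfare or data integrity. Enrolling an intended patient does not evidently do any of these. What remains is a mismatch on paper.
- *That the internal control is lost across the trial.* This needs surgery on the contralateral leg of a participant who has biopsies, and biopsies are optional in Aim 2. It does not reach the non-biopsy list.

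**Conclusion.** The concern holds as an inverted eligibility criterion in operative text. In both Aim 2 lists the negation conflicts with the exclusion heading and with the inclusion criterion, the adjacent exclusion and the role of the non-operative leg. Followed as written, it would select the wrong population, so it should be corrected even though the intent is easy to guess.

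The demonstrated effect is limited to a mismatch between written eligibility and intended practice. Any effect on the 6-month functional and patient-reported outcomes depends on literal use, which nothing shows, and on a second-arthroplasty rate that the documents do not give.

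The Aim 1 bullet has the same fault. Because Aim 1 is reported complete, correcting it serves the record only. The conclusion rests on two assumptions: that an exclusion list means what its heading says, and that the surrounding criteria reflect the intended population.

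**What to change.** Reconcile each bullet with its heading, in its own wording. Either delete *not* where the bullet stands, or move the sentence unchanged to the matching inclusion list. Keep the scopes separate: any other lower-limb total joint arthroplasty over 6 months for both Aim 2 lists, and contralateral TKA over 6 weeks for Aim 1. A single replacement sentence used in all three lists would widen the Aim 1 criterion.

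In the same edit, reconcile the phrase that puts the end of treatment at 6 months with the stated supplementation period and the stated end of follow-up.

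The cost is a small wording amendment in two live places, plus one for the record. Sample size, visits and analysis do not change.
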